2 PRIMARY OBJECTIVE

1. To determine the safety and tolerability of the use autologous volar fibroblasts to reprogram non-volar to KRT9-expressing volar epidermis in human participants.

SECONDARY OBJECTIVES

1. To measure non-invasively for epidermal thickening in sites of injection of volar fibroblasts compared to both non-volar fibroblast injection and vehicle only injection
2. To measure for molecular changes in excised injected skin (for example increases in KRT9).
3. To describe persistence of epidermal thickening in sites of injection of volar fibroblasts over time.
4. To evaluate the safety and efficacy of an intermittent, serial dosing regimen of the autologous volar fibroblasts.
5. To evaluate the efficacy of superficial wounding with a curette at the injection sites.

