
If a subject refuses consent for the tattoo marker, but is otherwise willing to complete all other study procedures, then we can use the palpated sacral hiatus, and initiation of the gluteal cleft as 2nd and 3rd universal landmarks. In addition, we will maximize the use of individual landmarks such as nevi, seborrheic keratoses, scars and hemangiomas which are found on human skin. In previous studies that the PI has performed(1), he has used exactly this method for the injection of hyaluronic acid to identify sites months later and had universal success at identifying injection sites. Also, to enhance our ability to identify sites we will not limit injections to one side of the buttocks (or non-buttocks area as above) to enhance the available number of landmarks and ensure proper identification in subsequent visits after the injection. Finally, we will frequently also consult clinical photographs (photographed with rulers) of the injection site taken on the day of injection to optimize our ability to correctly map injection sites.

We will avoid injection into the skin above the ischial tuberosity to minimize discomfort and risks of ulcers

Phase One: Single Dose Injection

After numbing the participant with anesthesia described in Visit 2, two of the sites will be injected with 0.7-0.8 mls of media (5% DMSO, 6% hetastarch and 2.5% human serum albumin) containing 30-40 million autologous fibroblasts into a small area about 3-4mm injection area subepidermally at the level of the epidermis-

dermis junction. The third site will be injected with the same volume of media containing no autologous cells.

Phase Two: Intermittent Dosing Regimen

We do not propose to increase the total number of cells injected, but to inject fewer cells more often. At the PI's discretion, the subject may receive injections of the dosing regimen or injections of 10% DMSO.

Two of the three treated sites will receive cells. A total of 4 injections may maximally occur; the first will always include cells for these sites. The remaining 3 injections may include vehicle and up to 10% DMSO instead of cells administered within 30 days after injection of cellular product.

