The third control site will not receive cells but instead be injected with the same volume of media or up to 10% DMSO, containing no autologous cells; it, may receive intermittent administration of vehicle media or up to 10% DMSO with the same schedule as above for the two sites receiving cells. The 10% DMSO media will be RIMSO-50, a FDA-approved product for the use in interstitial cystitis and delivered intravesically. The injections may be spaced in any manner over the 30 days. The dose volume will be determined on the basis of results from Phase One. A range of dose volumes may be tested but the total number of injected autologous fibroblasts will not exceed 30-40 million. As in Phase One, the dose will be prepared by appropriately trained and qualified personnel in the cellular therapy core and administered by the PI. We will be using an FDA approved product (RIMSO-50), because we unexpectedly found in our animal studies that the DMSO in our vehicle actually enhances cellular engraftment. We propose to inject no more than 10% DMSO at a volume of less than 1 ml into the skin not more than 3 times. We will only inject the areas where the vehicle or cells were previously injected (3 approximately 6 mm circles). We confirm that this study will not proceed until this Protocol Amendment is granted approval from the Johns Hopkins Medicine Institutional Review Boards.

The following information will be recorded by the investigator administering the cells (see Cell Administration sheet in Appendix V):

- Vial identification numbers
- Date of administration
- Times of administration
- Total cell dose
- Injection sites

Superficial skin scrapings are routinely done in dermatology and may be employed before or after we inject cells in order to potentially enhance tissue repair and regeneration. They might also occur during graft evaluations in subsequent visits. Scrapes will be done at injection sites using two gentle steady strokes of a sterile disposable #15 blade or curette. This wounding technique was specifically chosen to eliminate bleeding and infection risks.

Participants will be observed for 60 minutes following the cell administration for adverse events. At two points in this interval we will perform blood pressure and pulse measurements to monitor for an allergic reaction

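### In Phase Two the control site need not match the cell sites on medium or DMSO strength, and its repeat injections are optional, so the volar-versus-vehicle contrast can be confounded

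*Combined protocol and SAP*

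**What the plan says.** **Control site, Phase Two (section 5.2.4).** "The third control site will not receive cells but instead be injected with the same volume of media or up to 10% DMSO". For later injections, it "may receive intermittent administration of vehicle media or up to 10% DMSO with the same schedule as above for the two sites receiving cells".

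**Cell sites, Phase Two (section 5.2.4).** "A total of 4 injections may maximally occur; the first will always include cells for these sites". After that, "The remaining 3 injections may include vehicle and up to 10% DMSO instead of cells administered within 30 days after injection of cellular product". The choice of regimen is left to the PI and is worded by subject: "the subject may receive injections of the dosing regimen or injections of 10% DMSO". Spacing within the 30 days is free.

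**Media.** Section 8.1 (Preparation) gives the cell-carrying medium as 5% DMSO, 2.5% human serum albumin and 6% hetastarch in saline. The alternative is a 10% DMSO medium identified as RIMSO-50.

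**Phase One (section 5.2.4).** The third site receives an equal volume of the same medium without cells. There is no alternative medium.

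**Status of DMSO.** The reason given for using it is that "we unexpectedly found in our animal studies that the DMSO in our vehicle actually enhances cellular engraftment".

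**Where the control site is used.** Secondary objective 1 measures thickening at volar sites "compared to both non-volar fibroblast injection and vehicle only injection". The early-removal rule (sections 5.2.5 and 9.2) requires significant elevation at the volar site but not at the non-volar or vehicle-only site. The Phase Two schedule carries the same early-removal footnote. The only end-of-study t-test in section 9.2 compares volar with non-volar injections.

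**The concern.** A vehicle control isolates the effect of cells only if the vehicle site gets everything that the cell sites get except the cells. Phase One is written that way and Phase Two is not. If the control is given one medium and the cell sites another, the volar-minus-vehicle difference estimates the cell effect plus whatever the difference in medium does. The plan has no means of separating the two.

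The sponsor does not treat DMSO as inert: its reported effect on engraftment is the reason for adding it. Blinding the staff who measure thickness protects the reading of the images but does not remove a real difference in what the sites received.

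At stake are the vehicle half of secondary objective 1 in Phase Two (80 of the 100 planned subjects) and, to a lesser degree, early-removal designation in that phase.

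**Working it through.** **1. What is fixed and what is open, Phase Two, within one subject**

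| Component | Cell sites | Control site | Required to match? |
|---|---|---|---|
| Volume | as chosen | same volume | Yes |
| Timing of repeats | within 30 days | same schedule, if given | Yes, if given |
| Medium, first injection | 5% DMSO, albumin, hetastarch | media, or up to 10% DMSO | No |
| Medium, repeats | may be vehicle or up to 10% DMSO instead of cells | vehicle or up to 10% DMSO | No |
| Number of injections | up to 4 | repeats worded as optional | Not stated outright |
| Scraping | optional | optional | Not stated |

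**2. Size of the permitted difference in exposure**

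- One injection: 10% / 5% = 2-fold.
- Cumulative exposure, assuming equal volume at every injection and counting percent × injections. Section 5.2.4 limits 10% DMSO to three injections.
  - Four injections at every site (the natural reading): 5 + 3 × 10 = 35 against 4 × 5 = 20, so 35 / 20 = 1.75-fold. The text allows this in either direction.
  - Control given no repeats (the least natural reading): 35 against 5, so 7-fold.

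These are ratios of exposure, not of effect.

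**3. The plan's own figure**

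Section 9.2 assumes a difference of 2, SD 0.5, alpha 0.06 and power 0.8, and states that 3 participants suffice. With d = 2 / 0.5 = 4 and a two-sided unpaired t-test, the noncentral t gives power 0.63 at n = 2 per group and 0.96 at n = 3. The figure reproduces. It has no bearing on this point, because it does not concern matching of sites.

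**4. What a non-cell shift would do (illustration only)**

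The documents give no effect of DMSO or needling on thickness and name no end-of-study test for volar versus vehicle. Assume no cell effect, a constant non-cell shift of b SD between the sites, and an unpaired two-sided t-test at 0.05. Pairing within subjects is ignored. Then df = 2n − 2, the noncentrality is b√(n/2), and the chance of a significant result is P(|T| > t₀.₉₇₅). For b = 0.5 the noncentrality is 0.61 at n = 3, 1.58 at n = 20 and 3.16 at n = 80.

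| n per group | b = 0 | b = 0.25 | b = 0.5 | b = 1.0 |
|---|---|---|---|---|
| 3 | 0.05 | 0.06 | 0.08 | 0.16 |
| 20 | 0.05 | 0.12 | 0.34 | 0.87 |
| 80 | 0.05 | 0.35 | 0.88 | about 1.00 |

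Here 3 is the minimum in section 9.2, 20 is an intermediate value and 80 is full Phase Two enrolment. A larger sample does not dilute a shift of this kind; it makes a false conclusion more likely. If the mismatch varied in direction between subjects, it would act more as added noise than as a shift. If the stronger DMSO were at the control site and increased thickness there, it would mask a cell effect.

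**5. Could it be adjusted for afterwards?**

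The administration sheet (Appendix V) has columns for location, vial number, start and end times, and cell dose. A vial number might let the medium be traced, but there is no field for medium, DMSO strength or scraping.

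**6. A related inconsistency**

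The Phase Two outline in section 3 describes RIMSO-50 as 50% DMSO, while section 5.2.4 says that the 10% DMSO medium will be RIMSO-50. The two statements must be reconciled before DMSO strength can be matched or recorded.

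**The case against.** The best reply is that matching was plainly intended. Volume and schedule are stated to be the same. Repeats are optional at the cell sites too, so the control's optional wording most naturally mirrors a regimen chosen for the whole subject. The PI's discretion is worded by subject, and the text speaks of re-injecting the areas at all three sites. The only specified end-of-study test leaves out the control site. The early-removal rule also brings in the non-volar site: if both cell sites share a regimen, a non-cell effect should raise both and argue against designation.

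Most of this stands, and it limits the point in four ways.

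- A reader might infer that one control injection is planned beside four at the cell sites. The documents do not say so. They only fail to exclude it.
- A reader might infer that the volar and non-volar sites may also be treated differently. No sentence contemplates that; section 5.2.4 treats the two cell sites as a unit with one schedule.
- A reader might cite section 6.1.2 as evidence that DMSO alters skin at the planned strength. That section ties skin changes to very high doses and reports no adverse events with 5% DMSO in vehicle. The engraftment statement concerns injected cells, not thickening at a cell-free site.
- A reader might conclude that no difference could be attributed to volar fibroblasts. That goes too far, because the volar-versus-non-volar comparison remains.

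The reply does not close the gap on medium. The control's first injection is expressly one medium or another, no sentence links that choice to what the cell sites receive, and Phase One shows that the authors could fix it.

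**Conclusion.** The concern holds for medium and DMSO strength at the control site, which the text expressly leaves open. It holds more weakly for the number of control injections, which the optional wording leaves unsettled. It is confined to volar versus vehicle in Phase Two: part of secondary objective 1 and one element of the early-removal rule. Phase One is matched as written, and the end-of-study volar-versus-non-volar t-test is not affected through the control site.

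The permitted difference is 2-fold in DMSO strength at a single injection and, with four injections at every site and equal volumes, 1.75-fold cumulatively in either direction. Whether this moves epidermal thickness, by how much and which way, is unknown. The false-positive rates above are conditional on an assumed shift and are not estimates for this trial. The text should be corrected because it permits an avoidable bias in a stated comparison and the remedy is cheap.

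**What to change.** Add a rule to the Phase Two part of section 5.2.4: within each subject, whatever regimen is chosen, the three sites are matched at every injection visit on all non-cell components. These are medium and DMSO strength, volume, number and timing of injections, and any scraping. The sites then differ only in cell content: volar, non-volar or none. The same rule should cover scraping repeated at monitoring visits.

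Add per-site fields for medium, DMSO strength and scraping to the administration sheet in Appendix V, with the equivalent scraping entry for monitoring visits, so that departures are visible and can be examined in the analysis. Reconcile the two descriptions of RIMSO-50.

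The cost is a short protocol rule, a small form change and some loss of flexibility at site level. No extra visits or subjects are needed. Regimens can still vary between subjects, so the Phase Two aim of comparing delivery methods is kept; section 3 already describes curettage as applying to a subset of subjects. The choice of regimen stays with the sponsor.

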1 ABSTRACT

Cellular therapy holds great promise in medicine. This proposal will employ autologous fibroblasts in an attempt to help the more than 1.7 million (1 out of every 200) people in the US who have had limb amputations. While improvements in prosthetics have been made, their use is still dramatically limited by pain and skin-breakdown at the stump site. Our long-term goal is to permanently convert the skin at the stump site to **volar type (palmo-plantar)** skin. Volar epidermis is markedly thicker than skin at other locations and **uniquely** expresses Keratin 9 (KRT9) which makes it more friction- and irritant-resistant. We and others have shown that volar fibroblasts have the ability to increase epidermal thickness in 3-D and induce ectopic KRT9 **in non-volar keratinocytes** in both 2-D and 3-D co-cultures. (Given that KRT9 is a suprabasalar keratin, and unique to volar skin, it is an ideal read-out). Therefore our aim is a proof-of-concept demonstration

Hypothesis: Autologous volar fibroblasts have the capacity to induce ectopic volar gene expression such as KRT9 in human subjects. To investigate this, we intend to:

Phase One

1. Inject autologous volar and nonvolar fibroblasts in paired areas of the buttocks, or non-buttocks area. (All non-buttocks areas will exclude genitals, face, or at joints) Perform noninvasive imaging over a maximum period of 6 months to monitor for thickened epidermis/stratum corneum and longevity of effect. Also, if early thickening occurs, then we will remove injected skin area early in ½ of participants for #2.
2. Analyze epidermis by both histology and RT-PCR for features of volar phenotype (KRT9, epidermal thickness, stratum corneum thickness, presence of PAX9^{high}, LMX1b^{low}, EMX2^{low}, SHOX^{low} fibroblasts)

Phase Two

3. Identify optimal methods of delivery that will enhance skin reprogramming and improve conversion of non-volar to volar skin. We propose 2 testing methods with the goal of enhancing volar fibroblast stem cell engraftment: (a) We will investigate the efficacy of multiple, intermittent injections, while holding the total number of injected cells constant. (b) An additional approach is to lightly curette the skin at the injection sites to test if superficial wounding of the epidermis enhances volar fibroblast stem cell engraftment.

If successful, the results of this proposal will be a first to ectopically reprogram human skin identity.

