3. Inject autologous fibroblasts into stump site (in the current proposal we will first test healthy participants and not amputees)
4. Monitor for conversion to ectopic palmo/plantar skin

Phase Two – Proposed therapeutic outline:

1. Biopsy palmo/plantar skin at the sole of the foot and the scalp (or other area with suitable non-volar skin) (note higher KRT9 in native tissue in Fig 4 and KRT9 induction in Fig 5)
2. Expand autologous palmo/plantar fibroblasts

3. Inject autologous fibroblasts into stump site (in the current proposal we will first test healthy participants and not amputees)
4. Introduce intermittent dosing regimen of autologous fibroblasts (multiple injections vs. single injection) or RIMSO-50 injection (50% DMSO), and superficial wounding with a curette in a subset of subjects.
5. Monitor for conversion to ectopic palmo/plantar skin.

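### Phase Two claims a constant cell total, but its dosing rules do not secure one, so a single-versus-serial conclusion could reflect cell number or DMSO rather than schedule

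*Combined protocol and SAP*

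**What the plan says.** The Abstract states the Phase Two aim: "We will investigate the efficacy of multiple, intermittent injections, while holding the total number of injected cells constant". Secondary objective 4 is "To evaluate the safety and efficacy of an intermittent, serial dosing regimen of the autologous volar fibroblasts". The Phase Two outline in section 3 adds a comparison and an alternative: "Introduce intermittent dosing regimen of autologous fibroblasts (multiple injections vs. single injection) or RIMSO-50 injection (50% DMSO").

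The operative rules are in 5.2.4 under the Phase Two heading:

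- On the total: "We do not propose to increase the total number of cells injected, but to inject fewer cells more often", and later "the total number of injected autologous fibroblasts will not exceed 30-40 million". No target or minimum is given.
- On who gets what: at the PI's discretion, "the subject may receive injections of the dosing regimen or injections of 10% DMSO".
- On content: at most four injections are given, and only the first must contain cells. "The remaining 3 injections may include vehicle and up to 10% DMSO instead of cells".
- On DMSO: "no more than 10% DMSO at a volume of less than 1 ml into the skin not more than 3 times". The same section reports that animal work showed DMSO improving engraftment.

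Section 8.1 caps a transplant volume at 37.5 million cells in 0.75 mL, allows lower doses, and says intermittent doses are frozen separately. The Phase Two schedule table lists injections on days 30, 37, 42 and 59 but does not say which contain cells. Section 9.2 averages values across subjects and tests volar against non-volar sites. It names no regimen and no schedule contrast.

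**The concern.** A ceiling is not a constant. Two kinds of Phase Two subject fit the wording of 5.2.4.

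1. The cell dose is divided, and one or more of the later parts is replaced by vehicle or DMSO. The site then receives fewer cells than a single-dose site, and possibly more DMSO.
2. The full cell dose is given first and only vehicle or DMSO follows. The cell total is kept, but the subject says nothing about serial cell dosing.

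The sponsor's own text treats both cell number and DMSO as active. In 8.1 the dose is justified partly by an assay in which more cells gave more hair follicles, and 5.2.4 credits DMSO with better engraftment. If regimens that differ in these two respects are set against single dosing, or averaged together, a better or worse result cannot be put down to the schedule. What is at stake is the search for the best delivery method in Abstract item 3, and any reading of objective 4 as evidence for or against splitting the dose.

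**Working it through.** **The plan's own figures.** The plan gives no calculation for a schedule comparison. Its only power statement (9.2: difference 2, SD 0.5, alpha 0.06, power 0.8, 3 participants) belongs to the volar versus non-volar test. Read as a two-sided two-sample t-test, power is 0.63 with 2 per group and 0.963 with 3, so the figure of 3 reproduces. It has no bearing on schedule.

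**Inputs.**
- Cell ceiling: 37.5 million in 0.75 mL at 5% DMSO (8.1). The 30–40 million in 5.2.4 is the looser form.
- Intended dose: around 36 million (8.1, whose last step is 7.2 million × 5 = 36 million; the earlier steps are not examined here).
- Injections: at most 4, with cells required in the first only (5.2.4).
- Added DMSO: at most 10%, under 1 mL, at most 3 times (5.2.4).
- Assumptions: an equal four-way split, and Phase One volumes, because 5.2.4 leaves the Phase Two volume open.

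**Cell total, illustration only.** Total = ceiling × (injections containing cells) / 4.
- 1 of 4: 37.5 × 1/4 = 9.4 million
- 2 of 4: 18.75 million
- 3 of 4: 28.1 million
- 4 of 4: 37.5 million

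The range is 4-fold, and the low end is 9.375 / 36 = 26% of the intended dose. If the ceiling were per subject over two cell sites, the range would be 37.5 / 2 / 4 = 4.7 to 18.75 million, again 4-fold. Without the equal-split assumption the text sets no lower bound.

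**Ceiling as written.** 30 / 37.5 = 0.80 and 40 / 37.5 = 1.067, so the stated range runs from 20% below to 6.7% above the 8.1 figure.

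**DMSO, as volume of pure DMSO at one site.**
- One full cell dose: 0.75 mL × 5% = 0.0375 mL.
- Four quarter doses, all cells: 4 × 0.1875 mL × 5% = 0.0375 mL. Splitting alone does not change DMSO.
- Full cell dose, then three 10% injections at the limit: 0.0375 + 3 × 1 mL × 10% = 0.3375 mL, and 0.3375 / 0.0375 = 9.0.
- Quarter cell dose, then the same three: 0.0094 + 0.30 = 0.309 mL, and 0.309 / 0.0375 = 8.25.

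These are upper bounds, since each volume must be under 1 mL. They take the volume limit as applying to each site. If 1 mL were shared equally over three sites, the added DMSO would be 0.30 / 3 = 0.10 mL and the ratio (0.0375 + 0.10) / 0.0375 = 3.7.

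**What follows.** Cell total, DMSO and number of injections can all differ between single-dose and Phase Two sites. No rule in 5.2.4 or 9.2 keeps them equal or reports them apart. The effect on thickness or KRT9 is not estimated, because the documents give no dose-response for either.

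**The case against.** The strongest reply is that the text leans towards serial cells and DMSO as alternatives. Section 3 and 5.2.4 both join them with an *or*, and 5.2.4 times the later injections from a single cellular product. On that view the total stays constant and DMSO is a condition under test, not a confounder. No sentence describes dropping a planned cell dose, and subjects whose cultures fall short are discharged under 4.4.1. Section 8.1 also refers the regimen to a schema on page 4, which was not available for this review and may fix the content of each injection.

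Further points are fair. Objective 4 asks about the serial regimen itself and does not demand a comparison. Section 9 plans no schedule test, and 6.3.2 leaves formal optimisation of dose and frequency to a later trial. The administration sheet in Appendix V records cell dose by site, so totals could be reconstructed.

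Most of this stands, and it limits the point. A reader might infer that serial sites will in fact receive fewer cells. The documents permit that but do not say it, and the 4-fold figure needs both an assumed split and replaced doses. A reader might also infer that the trial's main results are confounded. They are not: the primary tolerability outcome does not depend on this, nor does the volar versus non-volar contrast within a subject when both cell sites get the same regimen.

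What the reply does not remove is the Abstract's promise and the single-versus-multiple framing in section 3, neither of which the dosing rules secure. If DMSO follow-up is a separate condition, 9.2 still has no label to keep it apart from serial cells. Appendix V has no column for volume or DMSO concentration.

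**Conclusion.** The point holds in a limited form. The plan claims a constant cell total for Phase Two, and the rules in 5.2.4 and 8.1 do not guarantee it. Any conclusion about single versus serial dosing could therefore reflect cell number or DMSO. The DMSO difference can reach about 9-fold at the permitted maximum, assuming Phase One volumes and a per-site limit. The cell-number difference is 4-fold only as an illustration, and the page-4 schema may narrow it. The consequence falls on the delivery-method aim and on comparative readings of objective 4. It merits an amendment, because the plan followed as written can mix regimens that differ in factors the sponsor considers active, and the cure is cheap.

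**What to change.** **In 5.2.4.** Record before the first injection which regimen each Phase Two subject is assigned: a single cell dose, serial cell doses, or a single cell dose followed by DMSO or vehicle. Set one planned cumulative cell total per cell site, the same for all regimens and within the existing cap, and state whether that cap is per site. Give DMSO only in addition to this total, never in place of a planned cell dose. If the page-4 schema already fixes the cell doses, make 5.2.4 say the same.

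**In Appendix V.** Add product, volume and DMSO concentration for each injection.

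**In 9.2.** Report results by planned regimen and do not pool DMSO-follow-up subjects with serial-cell subjects. Keep every subject in the planned regimen. Use the recorded cell total, and whether scraping was done, only for description or sensitivity analysis. Excluding sites that fell short of target would select on something that happens after treatment starts, such as doses stopped for reactions. State that any single-versus-serial comparison is descriptive, because regimens are not randomised and the number of injections is not matched.

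**Alternative.** If discretion to replace cell doses is kept, delete the constant-total claim and draw no conclusion about schedule.

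**Cost.** An amendment through the IRB and the IND, a few form fields, and less discretion for the PI. No cells beyond the present cap are needed.
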